 Yes  No	Include evaluation of drugs, devices, biologics, tobacco, or dietary supplements or data subject to FDA inspection?	The regulatory ancillary review will be assigned to your study by IRB staff Contact: [contact] See: https://policy.umn.edu/research/indide	Consider seeking approval prior to IRB submission.
 Yes  No	Require Scientific Review? Not sure? See guidance on next page.	Documentation of scientific merit must be provided. Contact: [contact]	
Approved by Gillette Scientific Review	Relate to cancer patients, cancer treatments, cancer screening/prevention, or tobacco?	Complete the CPRC application process. Contact: [contact]	
	Include the use of radiation? (x-ray imaging, radiopharmaceuticals, external beam or brachytherapy)	Complete the AURPC Human Use Application and follow instructions on the form for submission to the AURPC committee. Contact: [contact]	Approval from these committees must be received prior to IRB approval;
 Yes  No	Use the Center for Magnetic Resonance Research (CMRR) as a study location?	Complete the CMRR pre-IRB ancillary review Contact: [contact]	These groups

MEDICAL PROTOCOL (HRP-590)

PROTOCOL TITLE: Development of a robotic ankle assist device to improve mobility in individuals with movement disorders

VERSION DATE: 11/09/2022

 Yes  No	Include the use of recombinant or synthetic nucleic acids, toxins, or infectious agents?	Complete the IBC application via eprotocol.umn.edu Contact:	each have their own application process.
 Yes  No	Include the use of human fetal tissue, human embryos, or embryonic stem cells?	Contact OBAO for submission instructions and guidance	
 Yes  No Approved by Gillette Compliance Review	Include PHI or are you requesting a HIPAA waiver?	If yes, HIPCO will conduct a review of this protocol. Contact: [contact]	

1.0 Objectives

1.1 Purpose:

The purpose of this investigation is to establish the feasibility and efficacy of a lightweight, battery-powered ankle brace system (ABS) to improve mobility for individuals with cerebral palsy (CP).

- Aim 1: Complete a personal-use feasibility analysis of the ABS. This aim will be completed by collaborators at Northern Arizona University and BiOMOTUM, Inc. (prime site/sponsor), and activities will be covered by a separate IRB protocol.
- Aim 2: Gather feedback from Aim 1 to design and prototype a minimum viable ABS for use in clinical and community settings. This aim will be completed by collaborators at Northern Arizona University, Shirley Ryan Ability Lab, and BiOMOTUM, Inc., and activities will be covered by separate IRB protocols.
- Aim 3: Quantify the potential for an ABS to increase the effectiveness of clinical gait therapy by targeted *assistance* and *resistance* training. **This aim will be completed by Gillette Children's Specialty Healthcare (Gillette), and activities will be covered by this IRB protocol.**

2.0 Background

2.1 Significance of Research Question/Purpose:

Many of the 500,000 children in the United States with CP, the most common cause of pediatric physical disability, have difficulty walking and participating in physical activity. Half of all ambulatory children with CP lose the ability to walk independently in adulthood, indicating that the current approaches for treating these individuals do not result in meaningfully improved mobility over time.

Physical therapy (PT) is essential for treating CP, but the amount of PT is generally insufficient, and the delivery of PT can be inefficient. There is currently no viable way to provide a sufficient dose of PT that will lead to long-term improvements in mobility and reduce the negative physical and social outcomes related to limited mobility and reduced physical activity.

Due to the lack of available and sufficient treatment methods for improving mobility, the study team aims to establish the feasibility and efficacy of an ABS for *assistance* and *resistance* training. In the long-term, this research will improve our ability to optimize the prescription of wearable assistive devices to improve mobility and increase physical activity in individuals with movement disorders.

2.2 Preliminary Data:

MEDICAL PROTOCOL (HRP-590)

PROTOCOL TITLE: Development of a robotic ankle assist device to improve mobility in individuals with movement disorders

VERSION DATE: 11/09/2022

Past work completed by our collaborators has shown improvements in walking outcomes following treadmill and over-ground *assistance* interventions using a powered ABS. In a pilot study conducted using an instrumented treadmill, five participants with CP (5-30 years old) practiced walking at self-selected speeds with powered plantarflexor assistance. Participants exhibited a 19% reduction ($p<0.05$) in net metabolic cost of transport on average during treadmill walking with assistance compared to their baseline walking condition. Compared to baseline, participants also had reduced crouch by 14.4 ± 4 degrees ($p<0.05$) across the lower extremities, increased positive ankle power by $43.6 \pm 7.4\%$ ($p<0.05$), and decreased positive hip power by $29.2 \pm 6.0\%$ ($p<0.01$).¹ All these changes are biomechanically favorable.

Further, in a pilot study to test the powered ankle brace *resistance* therapy, participants completed 10 training sessions over 4 weeks with progressively increasing levels of resistance. Participants exhibited significantly improved (reduced) stance-phase ankle co-contraction by $29\% \pm 13\%$ ($p<0.04$) and a more normal plantarflexor muscle activation profile by $30\% \pm 15\%$ ($p<0.02$). Additionally, an increase in neural control complexity of walking after training was observed, which was significantly greater than a matched control group that underwent standard orthopedic and neurologic surgery alone. These improvements in neuromuscular control are indicative of a more mechanically efficient gait pattern, improved metabolic cost, and enhanced functional performance.^{2,3}

2.3 Existing Literature:

Children with CP frequently experience a downward trend of reduced physical activity and worsening gait, leading to a permanent decrease or loss in ambulatory ability.⁴ For children with CP, walking is drastically more energetically expensive than for their typically developing peers.⁵ Experts have called for new ways to elevate activity levels in children with movement disorders.^{6,7}

The ankle joint plays a critical role during walking, acting to stabilize, support, and propel the body.⁸ Activation of the ankle plantarflexor muscles is reduced, less modulated, and often accompanied by co-activation of the antagonist dorsiflexor muscles in most individuals with spastic CP. Reduced ankle performance during walking in children with CP is suggested as a primary contributor to the observed gait dysfunction.⁹ Ankle plantarflexors of children with CP produce 50% less positive joint work than in typical gait,¹⁰ resulting in a reliance on more proximally located muscles for forward progression.¹¹ These muscle activation characteristics likely contribute directly or indirectly to reduced energy exchange,¹² elevated metabolic cost of transport,¹³ and lower levels of physical activity¹⁴ in this patient population. Evidence suggests that addressing or augmenting the neuromuscular

MEDICAL PROTOCOL (HRP-590)

PROTOCOL TITLE: Development of a robotic ankle assist device to improve mobility in individuals with movement disorders

VERSION DATE: 11/09/2022

deficits at the ankle may allow children with CP to engage in greater amounts of habitual physical, which would likely have many additional physical and mental health benefits.^{15,16}

3.0 Study Endpoints/Events/Outcomes

3.1 Primary Endpoint/Event/Outcome:

Activities collected at Gillette and will be split into an Exploration phase and an Experimental phase (split into Experiments 1 and 2), each with different outcomes:

- Exploration: Qualitative participant assessment of device usability, device comfort, and ease of donning/doffing.
- Experiment 1: Number of steps with mean late stance (i.e., propulsive) ankle plantarflexor activity above pre-session baseline average activity of 5 heel raises
- Experiment 2: Preferred walking speed and similarity of muscle activity to the average unimpacted activity pattern calculated via cross-correlation coefficient

3.2 Secondary Endpoint(s)/Event(s)/Outcome(s):

- Exploration: N/A
- Experiment 1: Number of steps with mean stance phase ankle co-contraction below pre-session baseline
- Experiment 2: Metabolic cost; six-minute walk test (6MWT); timed up-and-go test (TUG); gait kinematics and kinetics; stride-to-stride variability of lower-extremity muscle activity; variance accounted for by the first muscle synergy; plantarflexor muscle strength; 66-item Gross Motor Function Measure (GMFM-66)

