15.0 Statistical Considerations

15.1 Data Analysis Plan:

Data will be collected and analyzed by Gillette study team members and collaborators.

Exploration:

As described below, the Exploration phase is a sample of convenience, and these activities are preparatory to the Experimental phase.

Experiments 1 and 2:

For Experiments 1 and 2, power analyses were used to determine estimated sample sizes. Statistical procedures include Repeated Measures ANOVA (RM-ANOVA) and generalized linear models. Participants in each Experiment will be age-, GMFCS-, and sex-matched as appropriate to control for known and unknown covariates. Participant demographics and baseline characteristics will also be analyzed.

15.2 Power Analysis:

Exploration:

No power analysis was done for the Exploration phase; this is a sample of convenience.

Experiment 1:

The sample size for the primary outcome measure in Experiment 1, mean stance phase plantar-flexor activity, was determined for the Repeated Measures ANOVA (RM-ANOVA). We set the Type II error rate (beta) at 0.2, and therefore the power level at 0.8 and alpha at 0.05. Sample size was determined based on the difference in soleus activity (45 ± 35%) from our collaborators preliminary ABS resistance validation study. We found that a subject sample size of n = 10 will

MEDICAL PROTOCOL (HRP-590)

PROTOCOL TITLE: Development of a robotic ankle assist device to improve mobility in individuals with movement disorders

VERSION DATE: 11/09/2022

allow us to find significance. We will enroll and collect complete data for 12 participants to provide an adequate sample for our investigation into participant characteristics that will be correlated with outcomes.

Experiment 2:

The sample size for the primary outcome measures in Experiment 2 was determined for the RM-ANOVA using our preliminary over-ground RAAD assistance training study (speed: $24\pm10\%$; normality of soleus profile: $39\pm20\%$; see section 2.2 Preliminary Data). We found that a sample size of $n = 5$ will allow us to find statistical significance for the assistance training protocol. We will enroll 12 participants to provide an adequate sample for our investigation into participant characteristics (i.e., covariates) that will be correlated with outcomes.

15.3 Statistical Analysis:

Exploration:

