Chief Science Officer

NCT04516343

**Title: Evaluation of the Safety and Efficacy of a Lower Extremity
BiOMOTUM Exoskeleton in the Pediatric Population with
Cerebral Palsy**

2/6/2025

Statistical Analysis Plan

Gait Training with RAAD assistance statistical analysis:

The RAAD assistance training protocol took place under the supervision of [name] at Gillette Children's Specialty Healthcare. We completed the protocol with 12 participants for this arm of the study. Participants completed a pre-training assessment and then 12 sessions (roughly 3 per week for 4 weeks) of RAAD assistance over-ground walking training. Walking speed was measured using a gait timer; the distance in meters was divided by the completion time in seconds. Walking distance was measured using a distance wheel measuring tool. To calculate the metabolic cost of transport, the standing baseline metabolic rate for each participant and each trial was subtracted from their walking metabolic rate to estimate the net metabolic rate of walking. Next, we normalized the net metabolic rate of walking by each participant's body mass and walking speed to calculate the metabolic cost of transport. Outcomes were assessed during walking without the RAAD before and within one week after the last training session. We checked outcome measures data for normality using a Shapiro-Wilks test. For data that were normally distributed, we tested for statistical differences using paired Student's T-tests (two tailed, alpha set to 0.05).

Gait Training with RAAD resistance statistical analysis:

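### Experiment 2 has two primary endpoints, but the SAP never defines or analyses the muscle-activity one, and neither document says whether one or both must succeed

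*Protocol*

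**What the plan says.** The Gillette protocol, section 3.1, gives Experiment 2 two primary outcomes: "Preferred walking speed and similarity of muscle activity to the average unimpacted activity pattern calculated via cross-correlation coefficient". Section 3.2 lists eight secondary items, beginning "Metabolic cost; six-minute walk test (6MWT); timed up-and-go test (TUG); gait kinematics and kinetics". Section 15.2 confirms that there is more than one primary: "The sample size for the primary outcome measures in Experiment 2 was determined for the RM-ANOVA". It quotes a pilot effect for speed (24 ± 10%) and one for normality of the soleus profile (39 ± 20%), and concludes that 5 participants are enough. Section 15.3 plans RM-ANOVA and has no multiplicity rule. Sections 4.1 and 5.2 schedule surface EMG at baseline and at both follow-ups.

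The SAP part on gait training with RAAD assistance is the same experiment: Gillette, over-ground training, 12 sessions, 12 participants. It describes three outcomes: "Walking speed was measured using a gait timer"; "Walking distance was measured using a distance wheel measuring tool"; and, for energy cost, "To calculate the metabolic cost of transport, the standing baseline metabolic rate for each participant and each trial was subtracted". The test is conditional: "For data that were normally distributed, we tested for statistical differences" by paired t-test, "two tailed, alpha set to 0.05". No test is named for other data. No outcome is labelled primary or secondary, and EMG, muscle activity and cross-correlation do not appear.

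**The concern.** Two primaries need a rule for what counts as success, and each needs a defined analysis. Here the rule is missing from both documents, and one of the two primaries has no definition in the SAP. Two things are at stake. First, if success on either primary would be called a positive result, two unadjusted tests at 0.05 give more than a 5% chance of a false claim. Second, someone who follows the SAP as written could report speed, distance and metabolic cost and leave out an endpoint that the protocol called primary and used to size the experiment. A reader of the report would then not know that it was missing.

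**Working it through.** **1. Reproduce the stated sample size.** Inputs from section 15.2: speed d = 24/10 = 2.40; soleus profile d = 39/20 = 1.95. This reads ± as an SD and takes the soleus-profile measure as the similarity primary. Alpha 0.05 and power 0.80 are stated under Experiment 1 and assumed to carry over. For a two-sided paired t-test, power is the probability that a noncentral t with n − 1 degrees of freedom and noncentrality d√n falls beyond ±t(1 − α/2, n − 1).

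- Speed: n = 4 is the smallest n with power of at least 0.80.
- Soleus profile: n = 5 (power 0.896).

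The larger is 5, the protocol's figure. So the stated n matches the requirement of the primary that the SAP leaves out.

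**2. False-positive rate if either primary suffices.** With two independent tests at 0.05 the rate is 1 − 0.95² = 0.0975. The documents give no correlation between the endpoints, so correlated values are assumptions. Simulated paired t-tests at n = 12 (50,000 runs each) gave:

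| Assumed correlation | At least one p < 0.05 |
|---|---|
| 0.3 | 9.6% |
| 0.5 | 9.2% |
| 0.8 | 8.0% |

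**3. False-positive rate if both are required.** A false claim needs every true null among the two to be rejected at 0.05, so the rate cannot exceed 5%. There is no inflation, but the SAP then lacks a specified analysis of half of the success criterion.

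**4. Effect of splitting alpha.** At 0.025 each, the familywise rate is 1 − 0.975² = 0.0494 if independent, and at most 0.025 + 0.025 = 0.05 in any case.

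| | α = 0.05 | α = 0.025 |
|---|---|---|
| Required n, speed | 4 | 5 |
| Required n, soleus profile | 5 | 6 |
| Power at n = 12, speed | > 0.9999 | > 0.9999 |
| Power at n = 12, soleus profile | > 0.9999 | 0.9999 |
| Detectable d at n = 12, 80% power | 0.89 | 1.01 |

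**5. Sensitivity to the ± reading.** If ± were a standard error from the six-person over-ground pilot (an assumption), the SD would be √6 times larger. Speed would have d = 24/(10√6) = 0.98, with power at n = 12 of 87% at 0.05 and 78% at 0.025. The soleus profile would have d = 39/(20√6) = 0.80, with power of 71% and 58%.

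**The case against.** The strongest reply is that the protocol already ranks its outcomes and the SAP does not revoke that ranking. Section 3.1 joins the two primaries with an and, and the stated n is the larger of the two requirements. Both facts fit a rule that both must succeed, under which nothing is inflated. The SAP also speaks of outcome measures in general, which could be taken to include the similarity measure. Much of this stands: inflation is conditional, and it is the definition and specific analysis of that primary that are missing. But a conjunction in an endpoint list is not a decision rule, and a general reference is thin for a primary when three other outcomes each get a method of measurement or calculation.

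Several stronger readings are tempting and are not supported.

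- A reader might infer that any outcome, including a secondary, could carry the efficacy claim, and compute 1 − 0.95⁸ = 33.7% for eight outcomes. The protocol separates primary from secondary, so the open choice is between the two primaries. Independence is also implausible: cost of transport is divided by walking speed, and the 6MWT and TUG are walking tests.
- A reader might say that the SAP tests everything at 0.05. The t-test is limited to normally distributed data.
- A reader might extend the point to the resistance arm. The Shirley Ryan AbilityLab protocol (Study Endpoints) names self-selected gait speed as its only efficacy primary, so no two-primary problem arises there.
- A reader might infer that the similarity endpoint was dropped because of its result. The SAP is dated 2/6/2025 and written in the past tense, but nothing in it says why the endpoint is absent.

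**Conclusion.** The point holds for Experiment 2 as a gap in endpoint definition and in the success rule. A protocol primary that helped set the sample size has no definition or specific analysis in the SAP, and neither document says whether one or both primaries must succeed. If either is enough, the error rate for the pair is up to 9.75%, or about 8.0% to 9.2% at assumed correlations of 0.8 to 0.5. If both are needed, it stays within 5%. Either way the SAP needs correction. This is not a sample-size problem: the stated n = 5 reproduces, and 12 participants exceed it. The statement that a split alpha costs almost no power rests on the pilot effects and on reading ± as an SD.

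**What to change.** In the SAP section on the assistance arm:

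- Carry over the protocol's primary and secondary labels.
- Define the muscle-activity similarity measure and its analysis, and report it whatever its result. If the EMG data were not obtained, document that instead.
- State the success rule. Either require both primaries at two-sided 0.05, or allow either one and control the pair by Holm or Bonferroni (0.025).
- Report the other Experiment 2 outcomes as secondary estimates with 95% confidence intervals.
- State that the rule was set after data collection. The SAP describes a completed arm, so the choice between the two rules should not draw on the results, and the SAP should say whether they were known.

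A fixed testing order, such as speed first, is not recommended. An order chosen at this stage does not protect the error rate, and the protocol ranks neither primary above the other. Holm and Bonferroni need no order.

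The cost is SAP wording plus one analysis of data whose collection was already planned. Under an either-primary rule with a 0.025 split, the threshold is slightly stricter: the detectable standardised effect at n = 12 and 80% power rises from 0.89 to 1.01. If ± was a standard error, the loss would be larger (71% to 58% for the similarity primary).

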4.0 Study Intervention(s)/Investigational Agent(s)

4.1 Description:

Both the Exploration and Experimental phases will test the use of the ABS within the context of device usability and ease (Exploration), therapy precision (Experiment 1), and assistance training (Experiment 2). Participants may partake in any study phase in which they are eligible, and participation in each experiment may take place in any order.

Exploration:

In the Exploration phase, participants will come to Gillette for up to two visits. These visits will include ABS fitting and acclimation to test device usability, device comfort, assisted vs. unassisted walking performance, and ease of

MEDICAL PROTOCOL (HRP-590)

PROTOCOL TITLE: Development of a robotic ankle assist device to improve mobility in individuals with movement disorders

VERSION DATE: 11/09/2022

donning/doffing. This exploratory work will allow participants to test the ABS, and a licensed physical therapist (PT) will be present. To explore a participant's accommodation to the device, the PT, at their discretion, may use electromyography, metabolic measurements, and/or 10 m and 6 minute-walk-tests. Participant, parent/guardian, and therapist questionnaires may be provided. If interested and eligible, they would be invited to participate in Experiments 1 and 2, although participation in the Exploration phase is not a requisite for participation in Experiments 1 and/or 2.

Experiment 1:

In Experiment 1, participants will come to Gillette for a baseline visit. This baseline visit will include ABS fitting and acclimation. Following the baseline visit, participants will return to Gillette for 3 additional visits in a randomized order: assistance visit, resistance visit, and typical gait therapy visit. During each visit, a licensed PT will guide participants through the following activities while collecting plantarflexor activity via surface electromyograph (EMG): 10 minutes of treadmill walking, 10 minutes of overground walking, and 15 minutes of walking skills practice (e.g., sideways, backward, stepping strategies, etc.).

Experiment 2:

In Experiment 2, participants will come to Gillette for a baseline visit. Like Experiment 1, this baseline visit will consist of ABS fitting and acclimation. Following the baseline visit, participants will return to Gillette for 12 visits with assistance training. Assistance training will include approximately 20-30 minutes of overground walking with assistance monitored by the PT; participants will complete three ~5-10-minute bouts of walking with seated rest periods in between. The research team will guide participants to walk at a moderate-to-high intensity for the duration of each walk as indicated by level 7 ("Hard") on the Pictorial Children's Effort Rating Table (PCERT).¹⁸

After all assistance training visits are complete, participants will complete follow-up visits at 3 days and 3 weeks post-training. At the baseline and follow-up visits, the participants will complete the following activities guided by a PT: standard three-dimensional gait analysis (e.g., metabolic cost, 6MWT, gait kinematics and kinetics, surface EMG, and physical examination), TUG, and GMFM-66 dimensions D and E (e.g., walking, running, and jumping activities).

MEDICAL PROTOCOL (HRP-590)

[figure not shown]
PROTOCOL TITLE: Development of a robotic ankle assist device to improve mobility in individuals with movement disorders

VERSION DATE: 11/09/2022

Participants must complete at least 1 visit per week and miss no more than 3 visits total.

4.2 Drug/Device Handling:

The ABS is a lightweight battery-powered ankle orthosis. The system includes a torque sensor, system controller, battery, cables, calf cuff and frame, foot plate, and sensor inserted in a shoe (Figure 1A). The complete ABS system has a total mass of 1.5 kg (70% of mass situated in a waist pack or backpack) and allows the user to move around freely (Figure 1B).

The ABS provides a small amount of motorized assistance that is intended to augment existing activity. This and other similar investigational devices have been classified by the Food and Drug Administration as a *nonsignificant risk device* because they do not meet the definition of significant risk under 812.3(m) of the investigational device exemption (IDE) regulation (21 CFR 812 and outlined in HRP-418 Checklist: Non-Significant Risk Device). In other words, the ABS:

- is not an implant;
- is not supporting or sustaining life;
- is not used for diagnosing/curing/mitigating/treating disease; and
- does not present the potential for serious risk to health or safety.

Additionally, several safety precautions are implemented to ensure participant safety, including mechanical “stops” to prevent hyperextension of joints, an emergency stop button that shuts off power to the device, and embedded software mechanisms that shut off power to the device if the user were to fall.

MEDICAL PROTOCOL (HRP-590)

PROTOCOL TITLE: Development of a robotic ankle assist device to improve mobility in individuals with movement disorders

VERSION DATE: 11/09/2022

Following 21 CFR 812.2 (as outlined in HRP-307 Worksheet: Medical Devices), the ABS fits within the *abbreviated IDE requirements* as:

- our activities are testing the safety and efficacy of the ABS;
- it is a nonsignificant risk device;
- it is not banned from use by the FDA; and
- informed consent and documentation of informed consent will be obtained from all participants. A comment of study participation will be made in the participants medical record as communication with other hospital staff.

Further, following the requirements for an abbreviated IDE, the investigator will follow regulations and reporting requirements as appropriate (21 CFR 812.150). At the end of the study, the investigator will be responsible for returning products to the prime site/sponsor and submitting a final report to the appropriate IRB.

4.3 Biosafety:

N/A

4.4 Stem Cells:

N/A

4.5 Fetal Tissue:

N/A

